**Exclusion criteria**

- Prior stenting or balloon dilatation within the previous 4 months
- Signs of bacterial cholangitis as defined by definite cholangitis according to the criteria in Supp Table 2 (Poinesen et al, Gastro 2015)
- Change of UDCA therapy within 4 weeks
- Inability to give informed consent
- Biliary cirrhosis with Child Pugh score  $\geq 8$
- Estimated transplant free survival < 2 years as calculated by Mayo score > 2
- Suspicion of cholangiocarcinoma, reflected by an imaging study suggestive of metastasis, MRCP with mass lesion with contrast enhancement, or rise in CA19.9 of > 63 U/ml in the previous 4 months together with an absolute value > 130 U/ml
- Signs of current malignancy other than basal cell carcinoma
- Life expectancy < 24 months
- Women pregnant at the time of screening
- HIV or acute or chronic hepatitis B or hepatitis C or substance (drug or alcohol) misuse within the previous 2 years.

**Interventions**

Eligible patients will undergo ERCP after informed consent. Periprocedural antibiotic prophylaxis will consist of intravenous piperacillin-tazobactam 4.5g or intravenous ciprofloxacin 500mg, and a subsequent dose 6 or 12 hours after.

Patients will be considered for the study only when, in the absence of purelant bile and fever > 38.5°C, 1 or more dominant stricture(s) of the common bile duct, the common hepatic duct and/or main left or right hepatic duct are encountered and deemed amenable to both balloon dilatation or stenting by the endoscopist. Before any intervention where possible, brush cytology will be obtained of any suspicious sominant stricture. If brush cytology demonstrates cholangiocarcinoma or high-grade dysplasia, that patient will be withdrawn from the study. Sphincterotomy will be performed at the discretion of the endoscopist.

[figure not shown]

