duct dilatation on imaging. Patients who develop high grade, clinically relevant strictures have an increased risk of cholangiocarcinoma, which can occur in up to 26% of patients with significantly reduced overall survival compared to those without high grade strictures (7). High grade strictures should be interrogated via ERC to investigate for the presence of a malignant stricture with tissue obtained via brushings for cytology and consideration of cholangioscopy and biopsy, which has higher sensitivity with comparable specificity (6, 8, 9).

In patients undergoing stenting in PSC, plastic stents are the primary intervention. These small-diameter stents can develop biofilms and occlude over time, possibly leading to cholangitis (10). Biodegradable stents are increasingly being used in a variety of indications (11, 12). They are a novel alternative that may confer benefit in the reduction of treatment-related adverse events by removing the necessity of repeat procedures for stent removal. They are made of polydioxanone (a synthetic biodegradable polymer). These stents have been clinically effective and safe in patients with symptomatic biliary obstruction (12, 13). They hydrolyse with variable degradation times. Similar to plastic stents, they have an introducer that allows placement over the target area, and positioning can be visualised fluoroscopically. The Archimedes stent is a commercially available biodegradable stent produced by AMG International (14). Clinical utilisation of these stents demonstrating excellent safety and efficacy are now emerging (12, 13).

In patients with PSC, endoscopic therapy of strictures aims to improve cholestasis by relieving the biliary obstruction via endoscopic biliary dilatation with consideration of plastic stents in strictures refractory to dilatation due to the risk of pancreatitis and cholangitis (15-17). Short term stents have been shown to have similar recurrence-free

rates compared to dilatation in a randomised control trial; however, this was terminated after interim analysis due to higher rates of serious adverse events in the stent group (15). The long term benefits are unclear; however, it may lead to improved survival compared to predicted survival (18). In this group of patients with limited treatment options, biodegradable stents may provide an attractive additional treatment modality in the management of high grade strictures.

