### **Primary endpoint**

Technical success and safety of biodegradable stent placement at ERC

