A high grade stricture is defined as a biliary stricture on MRCP with > 75% reduction of the duct diameter in the common bile duct or hepatic ducts. A relevant stricture is a high-grade biliary stricture on imaging in the common bile duct or hepatic ducts with signs or symptoms of obstructive cholestasis (rise in liver bloods tests, itch) and/or bacterial cholangitis.

All ERC and stent insertion attempts are to be carried out by an experienced operator. All procedures are to be carried out under general anaesthetic as per unit protocol. Medium degradation stents only to be used. All patients will receive intravenous Tazocin 4.5g pre/peri-procedure followed by 2 doses after. In the event of a penicillin allergy, intravenous Ciprofloxacin 500mg will be given with 2 further doses post procedure. All patients will be considered for pre/peri-procedural NSAID.

Patient information and informed consent will be obtained at ERC preassessment alongside physical examination and liver biochemistry. Insertion of the stent via ERC with endoscopist questionnaire on ease of placement, visibility on fluoroscopy, the maximum diameter of the stricture, whether dilatation was used and any procedure-related complications. Patient follow up on day one post insertion with questionnaires with a structured interview to assess for procedure-related symptoms and post-insertion AE. Liver function tests and telephone consultation on week 2 (up to 14 days post procedure) to assess for stent degradation, clinical response to therapy, complications and morbidity. MRCP at week 52 to assess for stricture remodelling with improvement in liver biochemistry. Patients will be closely monitored with access to the clinical team involved in the study. The pilot study will be carried out over 24 months.

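### The cytology rule can withdraw a patient after the stent is in, which ends follow-up and leaves that patient's place in the primary results undefined

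*Protocol*

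**What the plan says.** The withdrawal rule stands in the Protocol, section 3, Interventions: "If brush cytology demonstrates cholangiocarcinoma or high-grade dysplasia, that patient will be withdrawn from the study". It does not distinguish withdrawal before stenting from withdrawal after it. It does not say what happens to data already collected or whether follow-up continues.

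The sentence before it sets the timing of the sample: "Before any intervention where possible, brush cytology will be obtained of any suspicious" dominant stricture. The same paragraph brings patients into consideration when suitable strictures "are encountered and deemed amenable to both balloon dilatation or stenting by the endoscopist". A cytology result is not a condition of entry.

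The primary endpoint (section 2) is "Technical success and safety of biodegradable stent placement at ERC". The data for it are gathered early. Under Participants, the protocol describes "Insertion of the stent via ERC with endoscopist questionnaire on ease of placement", which also covers procedural complications, and then "Patient follow up on day one post insertion with questionnaires with a structured interview to assess for procedure-related symptoms and post-insertion AE". Later come a week-2 telephone contact with blood tests and an MRCP at week 52. The secondary endpoints include mortality, morbidity and local complications over 12 months.

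Under Sample size, 21 prospective patients form Group A, to be set against a historical balloon-dilatation Group B.

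**The concern.** The rule acts on a result that may arrive after the patient has received the device. Once the stent is placed, the protocol text schedules no further study treatment, only observation. Withdrawal at that point can therefore stop nothing but follow-up, and it does so while a degrading stent may still be in the duct.

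Two things are at stake. First, later safety information on an exposed patient would not be collected, and no later analysis can recover it. Second, one rule serves two purposes. Setting malignant strictures aside may be reasonable when the question is stricture recurrence. It is not reasonable when the question is whether the device can be placed safely, because the operator meets these strictures without knowing the result.

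**Working it through.** **Order of events in the text**

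1. ERCP is performed and a suitable dominant stricture is found (Interventions).
2. A suspicious stricture is brushed, before intervention where possible (Interventions).
3. The stent is inserted at ERC, technical data and complications are recorded, and the patient stays overnight (Participants; Stenting).
4. Adverse events are asked about on day 1 and again at week 2 (Participants).
5. The cytology result arrives at a time the protocol does not state. If positive, the patient is withdrawn.

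Nothing visible places step 5 before step 3. If it falls after step 3, the at-ERC data exist. Day-1 data usually exist too. Week-2 data exist only if the result comes later than that, and the 12-month data are cut short.

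A further gap follows from the Stenting section, which calls placement a failure after two unsuccessful ERCPs. A patient whose first attempt fails and who is withdrawn before a second is neither a success nor a failure under that rule.

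**The denominator**

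Inputs (Sample size): 55% vs 15%, two-sided alpha 0.05, power 80%, drop-out 15%.

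- n per group = [1.96·√(2·0.35·0.65) + 0.8416·√(0.55·0.45 + 0.15·0.85)]² / 0.40² = (1.322 + 0.515)² / 0.16 ≈ 21.1, rounded up to 22. The arcsine formula gives 20.5, rounded up to the stated 21. Power at 21 per group is 79.8%.
- Total with drop-out: 42 / 0.85 = 49.4, rounded up to 50.

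The stated figures reproduce closely enough. Group A enrolment is 21, the number before the drop-out allowance, so each patient is 1/21 = 4.8% of the denominator.

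**Chance that the rule is triggered**

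P(at least one) = 1 − (1 − p)^21. The rate p is assumed, since the documents give none.

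| Assumed p | Expected patients | P(at least one) |
|---|---|---|
| 5% | 21 × 0.05 = 1.05 | 1 − 0.95^21 = 66% |
| 10% | 21 × 0.10 = 2.1 | 1 − 0.90^21 = 89% |

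**Effect if such patients were left out of the primary results**

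*Precision.* If all placements succeed, the exact 95% lower limit is 0.025^(1/n): 83.9% for 21/21, 83.2% for 20/20, 82.4% for 19/19 and 81.5% for 18/18. The loss is small.

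*Selective loss.* These are invented cases, shown in both directions:

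| Full data | Left out | Result |
|---|---|---|
| 3/21 serious events, 14.3% (95% CI 3.0 to 36.3%) | 1 patient with an event | 2/20 = 10.0% |
| 3/21 | 2 patients with events | 1/19 = 5.3% |
| 3/21 | 1 patient without an event | 3/20 = 15.0% |
| 19/21 placed, 90.5% | 2 failures | 19/19 = 100% |
| 19/21 placed | 2 successes | 17/19 = 89.5% |

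With 21 patients, the choice of who is counted can move the headline figure by several percentage points either way.

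**The case against.** The strongest reply is that withdrawal from the study is not deletion from the analysis. The primary endpoint concerns the ERC itself. Procedural data are recorded on the day and adverse events are sought the next day, so most primary data would usually exist before a cytology result. Analysis sets are commonly left to the SAP, which is not at hand. This stands. A reader might infer that the protocol removes these patients from the technical-success and safety results. The text does not say so; it says neither that they are removed nor that they are kept. But an SAP cannot supply follow-up that the protocol has ended, and that part of the point survives.

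Three other stronger readings also fail:

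- A reader might take the Background figure, an "increased risk of cholangiocarcinoma, which can occur in up to 26% of patients", as the expected rate of positive cytology and compare the result with the 15% drop-out allowance. That figure is an upper value for cancer in patients with high-grade strictures, not a yield at one ERCP. The Exclusion criteria already remove suspected cholangiocarcinoma, and only suspicious strictures are brushed. The allowance is part of the 50 in total and is not visible in the 21 planned for Group A.
- A reader might infer that the rule flatters the stent because malignant strictures are harder to treat. Nothing in the protocol says that they carry more procedural risk than the benign strictures enrolled, so no direction can be claimed.
- A reader might infer that cancers are removed from Group A only. The protocol is silent on whether Group B is screened by cytology. Silence is not a stated asymmetry.

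The timing is also not documented. No cytology turnaround is given, and the figure under Interventions and the section 4 flow chart were not visible in the text available. If either shows stenting deferred until the result is known, the point largely falls away.

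**Conclusion.** The point holds in limited form. Followed as written, the rule permits a stented patient to be withdrawn, ends that patient's trial follow-up, and leaves the patient's place in the primary results open. At assumed rates of 5% to 10%, one or two of 21 patients would be affected, with a 66% to 89% chance of at least one. Because clinically suspected cancer is excluded beforehand, the true rate may be lower.

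This rests on two assumptions: that stenting can precede the result, which the visible text allows but does not state, and that withdrawal carries its ordinary meaning of ending trial observation. It is a defect in a stated rule that is cheap to repair, and not a demonstrated bias.

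**What to change.** Replace the withdrawal sentence with a rule on analysis and data collection that states:

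- Every patient with attempted stent placement stays in the technical-success and safety analyses, whatever the cytology shows. Say how a patient is counted whose only attempt failed before the result arrived.
- Adverse-event and mortality collection continues to 12 months after a positive result.
- The number of such patients and their outcomes are reported.
- If they are left out of the recurrence and re-intervention comparison, the same cytology exclusion is applied to the historical Group B, and the comparison is shown with and without it.

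None of this concerns the clinical care of these patients. The cost is a few sentences, slightly more follow-up data collection, and possibly a less favourable safety figure. Group B can be treated alike only as far as its records hold cytology results. Where they do not, the analysis without the exclusion is the one that treats both groups the same way.

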### **Stenting**

A 6Fr Archimedes (medium degradation) stent will be used for for strictures at the biliary hilum with consideration of bilateral stents if possible. 8Fr or 10Fr Archimedes (fast degradation) stents will be considered for dominant strictures in the common bile duct. Balloon dilatation (4mm or 6mm diameter) to facilitate stent placement will be allowed. If stent placement proved impossible after 2 ERCPs, then this will be classified as a failure. After the procedure, patients will be kept overnight for observation and intravenous antibiotics.

### **Ethical Consideration**

This study will be the first to analyse the feasibility of biodegradable stents in inflammatory liver pathology. The research protocol will be submitted to the Research ethics committee for approval. The study is to be conducted to ICH GCP standards.

#### 4. Study flow chart

MRCP, magnetic resonant cholangio-pancreatography; SOC, standard of care; ASSC, Amsterdam cholestatic complaint score; AXR, abdominal x ray.

